	
 
- Change from Baseline to Weeks 52 and 104 in FPG.
 
- Change from Baseline to Weeks 52 and 104 in BW.
 
- Proportion of patients with HbA1c <7.0% at Weeks 52 and 104.
 
- Proportion of patients starting rescue therapy during the 104 weeks of treatment.
 
- Change from Baseline to Weeks 26 and 104 in SBP for all patients.
 
- Change from Baseline to Weeks 12, 26, and 104 in SBP for the subset of patients with baseline SBP ≥130 mmHg and SBP <130 mmHg, respectively.
 
- Change from Baseline to Weeks 12, 26, and 104 in diastolic blood pressure (DBP) for all patients and the subsets of patients with Baseline DBP ≥80 mmHg and <80 mmHg, respectively.
 
- Changes from Baseline to Weeks 26, 52, and 104 in total body fat mass and total lean mass measured by DXA.
 
- Changes from Baseline to Weeks 26, 52, and 104 in serum estradiol (only for women).
 
- Changes from Baseline to Weeks 26, 52, and 104 in urinary albumin to creatinine ratio (UACR).
 
- Changes from Baseline to Weeks 26, 52, and 104 on estimated glomerular filtration rate (eGFR).
 

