##### **9.1.4.2 Blood pressure**

Systolic BP and DBP will be assessed at all on-site visits. Blood pressure measurements will be taken as described in [Section 9.2.1.6](#) with full details and directions for the measurement of BP and heart rate (HR) in [Appendix C](#).

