Potential therapeutic effect of sotagliflozin on BP reduction will be assessed in all trial patients. To avoid confounding factors, modification of antihypertensive medications is not allowed during the first 12 weeks of the Treatment Period. The beneficial effect of sotagliflozin to patients with inadequately controlled hypertension (patients with Baseline SBP  $\geq$ 130 mmHg or Baseline DBP  $\geq$ 80 mmHg) will be assessed, but also the impact of sotagliflozin in the BP of normotensive patients (patients with Baseline SBP <130 mmHg or Baseline DBP <80 mmHg) will also be assessed. Given the mechanism of action of sotagliflozin on renal tubular absorption of glucose and sodium, it is appropriate to assess the impact on calcium metabolism. For this reason, specific biomarkers for calcium metabolism and bone turnover will be assessed at several time points.

Decreases in bone mass measured by BMD have been reported with canagliflozin treatment and assessment of BMD changes will be a key safety endpoint for this study. The assessment of impact of treatment on bone mass will be performed by evaluation of BMD T-scores initially after 26 weeks of treatment to enable early detection of a bone safety signal and followed out yearly after the beginning of treatment. This duration of follow-up is appropriate to detect longitudinal trends in changes in bone mass in this population that is vulnerable to development of age-related bone loss.

Alterations in calcium homeostasis have been noted in nonclinical studies with selective SGLT2 inhibitors. Changes in calcium and bone biomarkers were evaluated in diabetic patients in Study LX4211.202, and no clinically significant changes on these parameters were observed. However, as changes in bone biomarkers have been observed in clinical studies of other selective SGLT2 inhibitors, the Sponsor will continue to evaluate bone biomarkers and events of fractures in the sotagliflozin clinical program.

It is recognized that weight loss is associated with reduction in bone mass and also reduction of estradiol levels in postmenopausal women. This study will include assessment of body composition to allow evaluation of differential changes in total body fat mass versus lean mass during the treatment. The change in levels of estradiol in women will be also assessed as adipose tissue is a major source of estradiol in postmenopausal women and decrease in these levels can be implicated in changes in bone turnover.

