## 11.4 STATISTICAL METHODS

Continuous data will be summarized by treatment group using the number of observations available (N), mean, SD, minimum, median, and maximum.

Categorical data will be summarized by treatment group using count and percentage.

In general, descriptive statistics of quantitative efficacy and safety parameters (result and change from Baseline) by scheduled visits will be provided on observed cases (OC), ie, inclusion of only patients having nonmissing assessments at a specific visit.

The Baseline value is defined generally as the last available value before the first dose of double-blind IMP or the last available value prior to randomization for patients who were randomized but never exposed to IMP.

For serum creatinine and eGFR, the Baseline value is defined as average of all values before the first dose of double-blind IMP for those randomized and exposed or before randomization for patients who were randomized but never exposed to IMP.

Analysis of demographics and Baseline characteristics and prior and concomitant medications will be provided in detail in the Statistical Analysis Plan (SAP).

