### **Measurement technique**

Following the 5-minute rest period, 3 separate seated BPs should be measured with at least 1 minute between BP measurements and with the cuff fully deflated between measurements.

All 3 BPs will be recorded in the patient's electronic case report form. The mean of the 3 seated BPs will constitute the BP value for that visit.

Three seated pulse rate measurements will be obtained. The mean of the 3 seated pulse rate measurements will constitute the pulse rate value for that visit.

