2.4.4.3 Analyses of other efficacy endpoints

The analysis of other endpoints (see [Section 2.1.3](#)) will be descriptive with no formal testing. Summary statistics at scheduled visits based on observed value will be provided by each treatment group. Graphical presentations will also be used to illustrate trends over time.

The number (%) of patients who used rescue therapy will be summarized by treatment group during the 26-week core (see [Section 2.5.4](#)) and the 104-week entire double-blind treatment periods. A KM curve for the time to first rescue therapy will be presented during the 26-week core treatment period and 104-week entire double-blind treatment period (see [Section 2.5.4](#)). The list of patients who used rescue therapy will also be provided.

UACR will be log-transformed at patient level. Summary statistics of UACR in log scale will be calculated for each treatment group at each visit and back-transformed to provide the geometric mean and its associated percent change of UACR from Baseline.

Shift tables will be provided for UACR at Week 26 and Week 104 respectively using the pre-defined categories. That is, the number (%) of patients with progression from one category at Baseline to another category at Week 26 and Week 104 will be provided by treatment group. The pre-defined categories are, for UACR, $<$ 30 mg/g creatinine [Normal], \geq 30 to $<$ 300 mg/g creatinine [Microalbuminuria], and \geq 300 mg/g creatinine [Macroalbuminuria].

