For the safety analyses, the baseline for a given parameter is defined as the last available measurement (or the average of all measurements for creatinine and eGFR), including unscheduled assessments, assessed prior to the first administration of double-blind IMP. For the efficacy analyses, the baseline for a given parameter is defined as the last available measurement (or the average of all measurements for eGFR), including unscheduled assessments, assessed prior to the first administration of double-blind IMP or the last available value (or the average of all measurements for eGFR) before randomization if not treated with double-blind IMP.

Summary statistics by visit for continuous efficacy endpoints

Summary statistics (number, mean, SD, SE, minimum, median, maximum) of continuous efficacy endpoints (observed data and change from Baseline) will be provided at scheduled visits as per protocol. Summaries showing data by visit will be presented according to the visit number (or re-allocated visit number, see [Section 2.5.4](#)) and labeled with the targeted approximate day/week.

Last on-treatment value for laboratory variables and vital signs

The last on-treatment value is the final measurement assessed during the treatment epoch, regardless of the introduction of rescue therapy, including measurements at unscheduled visits. See [Section 2.1.4](#) and [Section 2.5.4](#) for details.

Display of safety data by visit (laboratory variables and vital signs)

Descriptive statistics (number, mean, SD, minimum, median, maximum) of quantitative laboratory variables and vital signs (observed data and change from Baseline) during the TEAE period will be provided at scheduled visits. In addition, these summaries will also include a row for the 'last value on-treatment' to describe the last available on-treatment value (see above). Summaries showing data by visit will be presented according to the visit number (or re-allocated visit number, see [Section 2.5.4](#)) and labeled with the targeted approximate day/week.

As specified in the study protocol, laboratory data from scheduled visits are reported by central laboratories. The local results will not be used in the efficacy analyses or in the definition of

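### The blood-pressure subsets are cut on the same Baseline value that change is measured from, and no difference from placebo is planned for them, so their by-arm changes carry regression to the mean (minor)

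*Protocol*

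**What the plan says.** **Subsets.** The other objectives (Clinical Trial Summary and protocol 5.3) are framed as comparisons of each dose with placebo. They include "Change from Baseline to Weeks 12, 26, and 104 in SBP for the subset of patients with baseline SBP ≥130 mmHg", the complementary subset below 130 mmHg, and change in DBP for all patients and for "the subsets of patients with Baseline DBP ≥80 mmHg" and those below 80. SAP 2.4.4.2 adds a by-visit SBP summary for patients with baseline SBP of at least 140 mmHg.

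**Baseline.** Protocol 11.4 states: "The Baseline value is defined generally as the last available value before the first dose of double-blind IMP". SAP 2.5.4 uses the same rule and allows unscheduled pre-dose values. For most patients this will be Visit 3. Under Appendix C of the protocol, "The mean of the 3 seated BPs will constitute the BP value for that visit", so Baseline is a three-reading mean from one occasion.

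**Analysis.** Protocol 11.4.2.3 makes these endpoints descriptive, without formal testing. SAP 2.4.4.3 specifies the output: "Summary statistics at scheduled visits based on observed value will be provided by each treatment group". The summary of analyses in SAP Appendix C lists nothing more for the subsets than summary statistics and graphs.

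**Intended use.** Protocol 9.4 says that "The beneficial effect of sotagliflozin to patients with inadequately controlled hypertension" will be assessed, along with the impact in normotensive patients.

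**The concern.** A patient is placed at or above 130 mmHg partly because of true level and partly because that day's value was high. The second part does not persist, so the group mean falls at later visits whatever the treatment. The group below the cut rises for the same reason. Averaging three readings at one visit reduces within-visit noise but leaves visit-to-visit variation in place.

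A table of change by arm and subset therefore mixes drug effect with this artefact, in opposite directions on the two sides of the cut. A drug with a uniform effect could look strong in the high subset and nearly inert in the low one. What is at stake is how the effects named in protocol 9.4 are described, because the plan prints no contrast that would remove the artefact.

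**Working it through.** **Stated figure.** The documents give no figure for the blood-pressure subsets, so there is nothing to reproduce.

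**Inputs.** From the documents: cuts of 130 and 140 (SBP) and 80 (DBP); 120 patients per arm; and, as an illustrative effect, the -5.7 mmHg SBP reduction with 400 mg once daily reported from Phase 2 in protocol 4.2. Assumed: mean, SD and between-visit correlation (rho), shown as ranges.

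**Formula.** For a normal baseline with mean mu, SD s, cut c and z = (c - mu)/s:

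- Untreated change at or above the cut = -(1 - rho) × s × phi(z) / (1 - Phi(z))
- Untreated change below the cut = +(1 - rho) × s × phi(z) / Phi(z)

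**Central SBP case** (mean 135, SD 15, rho 0.65, cut 130):

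- z = -5/15 = -0.333; phi(z) = 0.377; Phi(z) = 0.369, so about 63% of patients are at or above the cut.
- At or above: the subset mean lies 15 × 0.377/0.631 = 9.0 above the overall mean; change = -0.35 × 9.0 = -3.1 mmHg.
- Below: the subset mean lies 15 × 0.377/0.369 = 15.3 below; change = +0.35 × 15.3 = +5.4 mmHg.

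**Ranges of untreated change (mmHg), rho 0.5 to 0.8:**

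| Assumptions | High subset | Low subset |
|---|---|---|
| SBP, cut 130; mean 130–140, SD 12–18 | -0.9 to -7.2 | +1.9 to +10.6 |
| DBP, cut 80; mean 74–80, SD 8–10 | -1.3 to -6.1 | +0.6 to +4.0 |
| SBP, at least 140; mean 135, SD 15 | -3.1 to -7.7 | no such subset |

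**Effect on the tables.** Simulation of the central case (2,000,000 patients), with a true effect of -5.7 mmHg in everyone:

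| Subset | Placebo | Sotagliflozin | Difference |
|---|---|---|---|
| 130 or above | -3.1 | -8.8 | -5.7 |
| Below 130 | +5.4 | -0.3 | -5.6 |

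The sotagliflozin column suggests a large effect in one subset and almost none in the other. The difference recovers the true effect in both, to within simulation error.

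**Precision of the missing contrast.** In the central case about 76 patients per arm are at or above 130 (120 × 0.631) and about 44 below (120 × 0.369). The baseline-adjusted residual SD is 15 × sqrt(1 - 0.65²) = 11.4. The 95% CI half-width is 1.96 × 11.4 × sqrt(2/76) = 3.6 mmHg in the high subset and 1.96 × 11.4 × sqrt(2/44) = about 4.7 to 4.8 mmHg in the low one, with no missing data.

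**Would reclassifying be minor?** "Systolic BP and DBP will be assessed at all on-site visits", so Visits 1 and 2 supply separate pre-dose values. If all visits share correlation r, Visit 3 correlates r / sqrt((1 + r)/2) with the mean of Visits 1 and 2. With mean 134, SD 14 and r = 0.6 this is 0.67, and the bivariate normal puts about 25% of patients on different sides of 130 under the two rules, about 91 of 360 (22% to 29% for r from 0.7 to 0.5).

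**The case against.** The strongest reply is that the trial has a concurrent placebo arm. Baseline precedes treatment, so regression to the mean is the same in every randomized arm in expectation and drops out of the comparison with placebo, which is the stated objective. The placebo column sits beside the active columns with N, mean, SD and SE, so a reader can subtract and form an unadjusted interval. This stands, and it limits the point to a missing output.

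The endpoints also carry no decision. They are descriptive and outside the testing hierarchy. The tested SBP endpoint, at Week 12, uses all patients, with ANCOVA on baseline and a placebo difference with 95% CI. This stands too.

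It could be said that a descriptive endpoint needs no model. That does not stand. SAP 2.4.4.1 calls its HbA1c subgroup analyses descriptive, yet estimates differences from placebo with SE and 95% CI from an ANCOVA with a treatment-by-subgroup term. One of those subgroup factors is baseline SBP cut at 130. SAP 2.4.5.1 does the same for BMD. As written, patients split at 130 mmHg get a placebo contrast for HbA1c but not for SBP.

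Two stronger readings should be set aside. A reader might infer that the plan will misstate the drug's effect in each subset. It would do so only if within-arm change were read without placebo, and protocol 9.4 says the effects will be assessed, not that they will be read that way. A reader might also infer that the low subset hides a falls or fracture signal. Protocol 4.4 ties susceptibility to hemodynamic events or falls to patients at high cardiovascular risk and with renal impairment in trials of other drugs, not to low baseline blood pressure. Low-pressure harm is also followed elsewhere: volume depletion as an event of special interest, the SBP abnormality criterion, common adverse events tabulated by baseline SBP, and adjudicated fractures.

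**Conclusion.** The point holds as a reporting gap of minor severity. The same Baseline value selects the subsets and anchors the change, only by-arm observed change is planned, and the comparison with placebo named in the objective is not an output for these subsets.

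The direction of the artefact follows from the design. Its size does not: about -1 to -7 mmHg at or above 130 and +2 to +11 mmHg below it rests on assumed means, SDs and correlations and on approximate normality. A lower correlation at later visits would enlarge the shift. The cancellation between arms holds in expectation for all randomized patients; these summaries use observed values, so dropout that differs by arm could disturb it.

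The documents do not support a claim that the primary or secondary tests, the type I error or the sample size are affected.

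**What to change.** In SAP 2.4.4.3, keep the protocol-defined subsets and add, for each subset and time point, the difference of each dose from placebo with 95% CI, presented descriptively and without testing. Use an ANCOVA with treatment, subset, treatment-by-subset, randomization strata, country and continuous baseline SBP or DBP, in line with the SAP's HbA1c and BMD subgroup analyses. Give the subset with baseline SBP of at least 140 mmHg the same contrast. Add one sentence saying that by-arm subset changes include regression to the mean and should not be read as drug effect.

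Do not reassign the subsets from Visits 1 and 2. The placebo contrast makes that unnecessary, and it would move about a quarter of patients and alter endpoints the protocol defines on Baseline.

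The cost is SAP wording and one added descriptive model, with no new data and no change to sample size or alpha.
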